SPECIAL NOTES ON RESPONSE ASSESSMENT

Patients with a global deterioration in health status requiring discontinuation of treatment without objective evidence of disease progression at that time should be reported as "symptomatic deterioration." Every effort should be made to document objective progression even after discontinuation of treatment. Symptomatic deterioration is not a descriptor of an objective response; it is a reason for stopping study therapy. The objective response status of such patients is to be determined by evaluation of target and non-target lesions as shown in Table 1 and Table 2.

For equivocal findings of progression (e.g., very small and uncertain new lesions; cystic changes or necrosis in existing lesions), treatment may continue until the next scheduled assessment. If at the next scheduled assessment, progression is confirmed, the date of progression should be the earlier date when progression was suspected.

REFERENCES

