Screening and subsequent tumor assessments must include CT scans (with oral and/or IV contrast unless contraindicated). A CT scan of the pelvis is required at screening and as clinically indicated or as per local standard-of-care at subsequent response evaluations. MRI scans with contrast of the chest, abdomen, and pelvis with a non-contrast CT scan of the chest may be used in patients for whom CT scans with contrast are contraindicated (i.e., patients with contrast allergy or impaired renal clearance).

A CT (with contrast) or MRI scan with contrast (if CT contrast is contraindicated) of the head must be done at screening to evaluate CNS metastasis in all patients. If CT with contrast is performed and the presence of brain metastases is considered equivocal, an MRI scan of the brain is required to confirm or refute the diagnosis of CNS metastases at baseline.

Patients with active or untreated symptomatic CNS metastases are not eligible for the study (see Section 4.1.2). Patients with untreated asymptomatic CNS metastasis at screening may be eligible. For untreated patients, brain MRI scan with contrast at screening is required, and need to meet all eligibility criteria as specified in Section 4.1.2.

If a CT scan for tumor assessment is performed in a positron emission tomography (PET)/CT scanner, the CT acquisition must be consistent with the standards for a full contrast diagnostic CT scan.

Venetoclax—F. Hoffmann-La Roche Ltd Page 93 of 214 Protocol GO41864, Version 2 Further investigations such as bone scans and CT scans of the neck should also be performed if clinically indicated. At the investigator's discretion, other methods of assessment of measurable disease as per RECIST v1.1 may be used.

Tumor assessments performed as standard-of-care prior to obtaining informed consent and within 28 days of Cycle 1, Day 1 may be used rather than repeating tests. All known sites of disease, including measurable and/or non-measurable disease, must be documented at screening and re-assessed at each subsequent tumor evaluation.

At subsequent (post-screening) tumor assessments, patients with a history of treated brain metastases at screening are not required to undergo brain scans unless clinically indicated (e.g., in patients with neurological symptoms). The same radiographic procedure used to assess disease sites at screening should be used throughout the study (e.g., the same contrast protocol for CT scans).

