6.5.2.1 Duration of Response

DOR, defined as the time from the first occurrence of a documented objective response to disease progression or death from any cause, whichever occurs first, as determined by the investigator according to RECIST v1.1 criteria. Data for patients without the occurrence of disease progression or death as of the clinical data cutoff will be censored at the time of the last tumor assessment.

The Kaplan-Meier approach will be used to estimate median DOR. The Kaplan-Meier curve of time to DOR will be provided. Only patients achieving a CR or PR will be included in the assessment of DOR.

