6.5.2.2 Progression-Free Survival

PFS after enrollment is defined as the time from enrollment to the first occurrence of disease progression or relapse or death from any cause (whichever occurs first), as determined by the investigator according to RECIST v1.1 criteria. Data for patients without the occurrence of disease progression or death as of the clinical data cutoff date will be censored at the time of last tumor assessment (or the time of enrollment plus 1 day if no tumor assessment was performed after the baseline visit).

The Kaplan-Meier approach will be used to estimate median PFS. The Kaplan-Meier curve of time to PFS will be provided.

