- P All patients will be tested for HIV prior to the inclusion into the study and HIV-positive patients will be excluded from the study. Patients with active hepatitis B (chronic or acute; defined as having a positive HBsAg test result at screening) will be excluded from the study. Patients with past or resolved HBV infection (defined as the presence of HBcAb and absence of HBsAg) are eligible; HBV DNA should be obtained in these patients prior to enrollment. Patients with HCV will be excluded from the study; patients who test positive for HCV antibody are eligible only if PCR is negative for HCV RNA.
- ^q Urinalysis by dipstick (specific gravity, pH, glucose, protein, ketones, and blood). Urinalysis is required at screening and will be obtained when clinically indicated.
- ^r For atezolizumab, the initial dose will be administered over 60 (±15) minutes. If the first infusion is well tolerated, subsequent infusions may be administered over 30 (±10) minutes (see Section 4.3.2.1). Venetoclax is administered QD for 21 days as described in Section 3.1.2; also see Section 4.3.2.2.
- ^s During the maintenance phase, PCI is permitted as per local standard of care and will be reported on the Prophylactic Cranial Irradiation eCRF.
- ^t CT scans (with oral/IV contrast unless contraindicated) or MRI scans of the chest and abdomen. A CT or MRI scan of the pelvis is required at screening and as clinically indicated or as per local standard of care at subsequent response evaluations. A CT (with contrast) or MRI scan of the head must be done at screening to evaluate CNS metastasis in all patients.
- ^u Perform every 6 weeks (± 7 days) for 48 weeks following Cycle 1, Day 1 and then every 9 weeks (± 7 days) thereafter, after completion of the Week 48 tumor assessment, regardless of treatment delays, until radiographic disease progression per RECIST v1.1, withdrawal of consent, death, or study termination by the Sponsor, whichever occurs first. Patients who continue treatment beyond radiographic disease progression per RECIST v1.1 will undergo tumor assessments *at the frequency described above* until study treatment is discontinued.

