Chest CT is preferred over chest X-ray, particularly when progression is an important endpoint, since CT is more sensitive than X-ray, particularly in identifying new lesions. However, lesions on chest X-ray may be considered measurable if they are clearly defined and surrounded by aerated lung.

CT AND MRI SCANS

CT is the best currently available and reproducible method to measure lesions selected for response assessment. In this guideline, the definition of measurability of lesions on CT scan is based on the assumption that CT slice thickness is ≤ 5 mm. When CT scans have slice thickness of >5 mm, the minimum size for a measurable lesion should be twice the slice thickness. MRI is also acceptable.

If prior to enrollment it is known that a patient is unable to undergo CT scans with intravenous (IV) contrast because of allergy or renal insufficiency, the decision as to whether a non-contrast CT or MRI (without IV contrast) will be used to evaluate the patient at baseline and during the study should be guided by the tumor type under investigation and the anatomic location of the disease. For patients who develop contraindications to contrast after baseline contrast CT is done, the decision as to whether non-contrast CT or MRI (enhanced or non-enhanced) will be performed should also be based on the tumor type and the anatomic location of the disease, and should be optimized to allow for comparison with the prior studies if possible. Each case should be discussed with the radiologist to determine if substitution of these other approaches is possible and, if not, the patient should be considered not evaluable from that point forward. Care must be taken in measurement of target lesions and interpretation of

non-target disease or new lesions on a different modality, since the same lesion may appear to have a different size using a new modality.

ENDOSCOPY, LAPAROSCOPY, ULTRASOUND, TUMOR MARKERS, CYTOLOGY, HISTOLOGY

Endoscopy, laparoscopy, ultrasound, tumor markers, cytology, and histology cannot be used for objective tumor evaluation .

ASSESSMENT OF TUMOR BURDEN

To assess objective response or future progression, it is necessary to estimate the overall tumor burden at baseline and use this as a comparator for subsequent measurements.

IDENTIFICATION OF TARGET AND NON-TARGET LESIONS

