If a new lesion is equivocal, for example because of its small size, continued therapy and follow-up evaluation will clarify if it represents truly new disease. If repeat scans confirm

Atezolizumab—F. Hoffmann-La Roche Ltd Page 180 of 214 Protocol GO41864, Version 2 there is definitely a new lesion, progression should be declared using the date of the initial scan.

CRITERIA FOR OVERALL RESPONSE AT A SINGLE TIMEPOINT

 Table 1 provides a summary of the overall response status calculation at each response assessment timepoint for patients who have measurable disease at baseline.

Table 1Criteria for Overall Response at a Single Timepoint: Patients
with Target Lesions (with or without Non-Target Lesions)

Target Lesions	Non-Target Lesions	New Lesions	Overall Response
CR	CR	No	CR
CR	Non-CR/non-PD	No	PR
CR	Not all evaluated	No	PR
PR	Non-PD or not all evaluated	No	PR
SD	Non-PD or not all evaluated	No	SD
Not all evaluated	Non-PD	No	NE
PD	Any	Yes or no	PD
Any	PD	Yes or no	PD
Any	Any	Yes	PD

CR = complete response; NE = not evaluable; PD = progressive disease; PR = partial response; SD = stable disease.

Table 2Criteria for Overall Response at a Single Timepoint: Patients
with Non-Target Lesions Only

Non-Target Lesions	New Lesions	Overall Response
CR	No	CR
Non-CR/non-PD	No	Non-CR/non-PD ^a
Not all evaluated	No	NE
Unequivocal PD	Yes or no	PD
Any	Yes	PD

CR=complete response; NE=not evaluable; PD=progressive disease.

^a "Non-CR/non-PD" is preferred over "stable disease" for non-target disease since stable disease is increasingly used as an endpoint for assessment of efficacy in some trials; thus, assigning "stable disease" when no lesions can be measured is not advised.

MISSING ASSESSMENTS AND NOT EVALUABLE DESIGNATION

When no imaging/measurement is done at all at a particular timepoint, the patient is not evaluable at that timepoint. If measurements are made on only a subset of target lesions at a timepoint, usually the case is also considered not evaluable at that timepoint, unless a convincing argument can be made that the contribution of the individual missing lesions would not change the assigned timepoint response. This would be most likely to happen in the case of PD. For example, if a patient had a baseline sum of 50 mm with three measured lesions and during the study only two lesions were assessed, but those gave a sum of 80 mm, the patient will have achieved PD status, regardless of the contribution of the missing lesion.

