Dyspnea, cough, fatigue, hypoxia, pneumonitis, and pulmonary infiltrates have been associated with the administration of atezolizumab. Patients will be assessed for pulmonary signs and symptoms throughout the study and will have CT scans of the chest performed at every tumor assessment.

All pulmonary events should be thoroughly evaluated for other commonly reported etiologies such as pneumonia or other infection, lymphangitic carcinomatosis, pulmonary embolism, heart failure, chronic obstructive pulmonary disease, or pulmonary hypertension. Management guidelines for pulmonary events are provided in Table 1.

Table 1Management Guidelines for Pulmonary Events, Including
Pneumonitis

Event	Management
Pulmonary event, Grade 1	 Continue atezolizumab and monitor closely. Re-evaluate on serial imaging. Consider patient referral to pulmonary specialist.
Pulmonary event, Grade 2	 Withhold atezolizumab for up to 12 weeks after event onset. ^a Refer patient to pulmonary and infectious disease specialists and consider bronchoscopy or BAL. Initiate treatment with corticosteroids equivalent to 1–2 mg/kg/day oral prednisone. If event resolves to Grade 1 or better, resume atezolizumab. ^b If event does not resolve to Grade 1 or better while withholding atezolizumab, permanently discontinue atezolizumab and contact Medical Monitor. ^c For recurrent events, treat as a Grade 3 or 4 event.
Pulmonary event, Grade 3 or 4	 Permanently discontinue atezolizumab and contact Medical Monitor. ^c Bronchoscopy or BAL is recommended. Initiate treatment with corticosteroids equivalent to 1–2 mg/kg/day oral prednisone. If event does not improve within 48 hours after initiating corticosteroids, consider adding an immunosuppressive agent. If event resolves to Grade 1 or better, taper corticosteroids over ≥ 1 month.

BAL=bronchoscopic alveolar lavage.

- ^a Atezolizumab may be withheld for a longer period of time (i.e., >12 weeks after event onset) to allow for corticosteroids (if initiated) to be reduced to the equivalent of ≤10 mg/day oral prednisone. The acceptable length of the extended period of time must be agreed upon by the investigator and the Medical Monitor.
- ^b If corticosteroids have been initiated, they must be tapered over ≥ 1 month to the equivalent of ≤ 10 mg/day oral prednisone before atezolizumab can be resumed.

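### PFS and DOR are censored at the last tumor assessment whether or not it was evaluable, and the passages on contrast and chest imaging disagree

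*Combined protocol and SAP*

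**What the plan says.** **Censoring.** Under Section 6.5.2.2, PFS for patients without progression or death is "censored at the time of last tumor assessment"; enrollment plus 1 day is used only if no assessment was performed after baseline. Under Section 6.5.2.1, DOR data "will be censored at the time of the last tumor assessment". Neither section mentions evaluability.

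**Not-evaluable ratings.** In Appendix 5, NE is one of the possible overall responses at a timepoint. If only some target lesions are measured, "usually the case is also considered not evaluable at that timepoint", unless the missing lesions could not change the result. If contrast becomes contraindicated and discussion with the radiologist finds no possible substitute, "the patient should be considered not evaluable from that point forward".

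**Scan schedule.** Section 4.5.5 requires scans every 6 weeks for 48 weeks, then every 9 weeks, until RECIST progression, withdrawal of consent, death or study termination. An NE rating does not stop them.

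**Imaging when contrast cannot be given.** Section 4.5.5 says "MRI scans with contrast of the chest, abdomen, and pelvis with a non-contrast CT scan of the chest may be used". Where the contraindication is known before enrollment, Appendix 5 leaves open "whether a non-contrast CT or MRI (without IV contrast) will be used". Where it arises after baseline, Appendix 5 allows non-contrast CT, or MRI with or without enhancement. Footnote t of Appendices 1 and 2 allows CT "or MRI scans of the chest and abdomen" for anyone. Appendix 13 (pulmonary events) says that patients "will have CT scans of the chest performed at every tumor assessment".

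**The concern.** A censoring date should be the last time the patient was shown to be free of progression. An NE scan does not show this for target lesions. If it still counts as the last tumor assessment, the patient stays in the Kaplan-Meier risk set while one main route to an event is closed. The effect on PFS, the 6-month PFS rate and DOR is then upward. Because partial measurement of target lesions is enough for an NE rating, the gap can touch any patient, not only those who lose contrast.

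The imaging passages matter because Section 4.5.5 sends the investigator to its own list of modalities and to Appendix 5 in the same sentence. The two lists differ, and only Appendix 5 has a patient-level NE outcome.

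**Working it through.** **1. Does the wording let an NE scan count?**

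- A scan with incomplete target measurement is still an assessment that was performed, and Appendix 5 gives it an overall response, namely NE.
- The PFS fallback turns on whether an assessment was performed, not on whether it was evaluable.
- Scanning continues after an NE rating, so later assessment dates arise.

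The literal reading therefore accepts NE scans, although no sentence says so. A patient last evaluable at Week 6 and scanned as NE to Week 48 would be credited with 48 − 6 = 42 further weeks.

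**2. How large could the effect be?**

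The plan states no figure for this. Inputs:

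- 20 expansion patients (Section 6.1)
- Kaplan-Meier estimate at 6 months (Section 6.5.2.4)
- median PFS 5.2 and median OS 12.3 months, from the randomized Phase III study of atezolizumab plus chemotherapy in Section 1.2, used as an assumption with exponential times
- number of NE patients: not in the documents; 1 to 4 of 20 assumed.

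*Simple arithmetic.* S(6) = 0.5^(6/5.2) = 0.449. Each patient counted event-free at 6 months adds (1 − 0.449)/20 = 0.028, about 2.8 points. Two add 0.055.

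*Worked example.* Take 2 events before Week 6, 9 more before month 6, and m NE patients with no event after Week 6. If NE scans count, the estimate is 9/20 = 45.0%. If censoring is at the last evaluable scan (Week 6), it is 0.9 × (9 − m)/(18 − m).

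| m | Last evaluable scan | NE scans counted | Difference (points) |
|---|---|---|---|
| 1 | 42.4% | 45.0% | 2.6 |
| 2 | 39.4% | 45.0% | 5.6 |
| 3 | 36.0% | 45.0% | 9.0 |

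*Simulation.* 2000 trials of 20 patients, scans on the plan's schedule, data cutoff at 24 months, NE from Week 6, no progression recordable once NE. With NE scans counted, deaths remain events.

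| NE patients | Last evaluable scan | NE scans counted | Difference (points) |
|---|---|---|---|
| 1 | 46.7% | 47.6% | 0.9 |
| 2 | 46.5% | 48.2% | 1.7 |
| 3 | 46.5% | 49.2% | 2.7 |
| 4 | 46.3% | 49.8% | 3.5 |

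The typical median PFS was 5.52 months either way, which is the Week 24 scan (24 × 7 × 12/365.25).

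Two limits apply. The simulation bars all progression once NE, which is stricter than Appendix 5. Its evaluable-scan column also censors NE patients at Week 6 even if they die later, whereas the plan would count the death. At 24 months, 0.5^(24/12.3) = 0.26 would be alive. With a late cutoff, new censoring wording would thus act on about a quarter of such patients, and with an earlier cutoff on more. The differences show the exposure, not the exact effect of the new wording.

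**3. The imaging passages side by side**

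| Place | Situation | Imaging |
|---|---|---|
| Section 4.5.5 | CT contrast contraindicated | MRI with contrast plus non-contrast chest CT (permitted, not required) |
| Appendix 5 | Contraindication known before enrollment | Non-contrast CT, or MRI without IV contrast |
| Appendix 5 | Contraindication arising after baseline | Non-contrast CT, or MRI with or without enhancement; NE if no substitute is possible |
| Appendices 1 and 2, footnote t | Any patient | CT or MRI of chest and abdomen |
| Appendix 13 | Any patient | Chest CT at every assessment |

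Rows 1 and 2 conflict on contrast. Row 4 is looser than rows 1 and 5 on chest CT. Rows 1 and 3 overlap.

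**The case against.** The strongest reply is that this is a gap in wording with a small effect on secondary, single-arm, descriptive endpoints. At S = 0.449 and n = 20 the 90% CI half-width is about 1.645 × √(0.449 × 0.551/20) = 0.18, or 18 points, far above the average shift. That stands as a limit on size.

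Four stronger readings are tempting, and the documents do not support them:

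- *The plan counts NE scans as progression-free time.* A reader might infer this as a stated rule. Sections 6.5.2.1 and 6.5.2.2 neither include nor exclude NE scans; counting them is the literal reading.
- *Patients without IV contrast become permanently NE.* Appendix 5 makes this a last resort after discussion with the radiologist. The clear conflict on contrast concerns contraindications known before enrollment, and those patients must already have measurable disease at baseline. For later contraindications, Appendix 5 also allows enhanced MRI.
- *An NE patient cannot progress.* In the Appendix 5 response table, a new lesion or non-target progression gives PD whatever the target status. Partial measurement can also establish PD, and death is always an event.
- *An NE patient is an ORR non-responder.* Section 6.5.1 names only patients with no disease assessments. A response confirmed before the NE rating stands. A patient who becomes NE before confirmation cannot confirm, which costs 1/20 = 5 points at worst.

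What remains is that the rule, applied as written, admits NE scans, and that the imaging passages differ.

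**Conclusion.** The point holds in limited form. As worded, the PFS and DOR rules allow a not-evaluable scan to extend progression-free follow-up, and the direction is upward. With 1 to 4 NE patients of 20 assumed, the 6-month PFS estimate rises by about 1 to 3.5 points on average. For each NE patient who is in fact carried event-free past 6 months the rise is about 2.8 points (2.6 to 3.0 per patient in the worked example). Median PFS is little affected. These sizes rest on first-line median PFS and OS, exponential times, NE status from Week 6 and a patient count that the documents do not give; a maintenance-only expansion could differ. No effect on DOR was calculated.

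The imaging passages are inconsistent and need reconciling in their own right. Their link to the NE outcome is weak.

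**What to change.** In Sections 6.5.2.1 and 6.5.2.2, replace the censoring date with the date of the last tumor assessment with an overall response other than NE. For PFS, use enrollment plus 1 day if there is no such assessment after baseline. DOR needs no fallback, because the response itself is an evaluable assessment.

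Separately, reconcile Section 4.5.5, Appendix 5 (CT and MRI scans), footnote t of Appendices 1 and 2, and Appendix 13 (pulmonary events) into one imaging rule, and refer to it from each place. It should cover contraindications known before enrollment and those arising later, say whether chest CT is required at every assessment, and state when a patient becomes NE. Which modality is right is for the sponsor to decide.

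The cost is a few sentences, and the censoring change needs no additional scans. PFS and DOR estimates may be slightly less favourable.

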Appendix 6 Examples of Prohibited and Cautionary Medications

CYP3A Inhibitors		CYP3A Inducers	
Strong	Moderate	Strong	Moderate
boceprevir	aprepitant	apalutamide	bosentan
clarithromycin	ciprofloxacin	carbamazepine	efavirenz
cobicistat	conivaptan	enzalutamide	etravirine
danoprevir	crizotinib	mitotane	phenobarbital
dasabuvir	cyclosporine	phenytoin	primidone
elvitegravir	diltiazem	rifampin	
idelalisib	dronedarone	St. John's Wort	
indinavir	erythromycin		
itraconazole	fluconazole		
ketoconazole	fluvoxamine		
lopinavir	imatinib		
nefazodone	tofisopam		
nelfinavir	verapamil		
ombitasvir			
paritaprevir			
posaconazole			
ritonavir			
saquinavir			
telaprevir			
telithromycin			
tipranavir			
troleandomycin			
voriconazole			

Table 1 Examples of Strong and Moderate CYP3A Inhibitors and Inducers

^a These are anti-cancer agents; consult the Medical Monitor before use.

Refer to Section 4.4.2 for guidance related to prohibited and cautionary medications.

